**Presentation of Visits**

CRF visits (visits as recorded in the eCRF) will be represented as follows and in that order:

Long Name (default)	Short Name
Screening	Scr
Baseline	BL
Week 1	W1
Week 4	W4
Week 8	W8
Week 9	W9
Week 12	W12
Week 16	W16
Early Withdrawal	EW
Follow Up	FU
Unscheduled Visit	US

CRF visits will be displayed in the listings. Analysis baseline defined in SAP will be flagged and will be identified in the listings as needed.

Analysis visits will be displayed in the tables.

## APPENDIX 2. PARTIAL DATE CONVENTIONS

Imputed dates will NOT be presented in the listings.

Algorithm for Treatment Emergence of Adverse Events:

START DATE	STOP DATE	ACTION
Known	Known	If start date < study med start date, then not TEAE If start date >= study med start date, then TEAE
	Partial	If start date < study med start date, then not TEAE If start date >= study med start date, then TEAE
	Missing	If start date < study med start date, then not TEAE If start date >= study med start date, then TEAE
Partial, but known components show that it cannot be on or after study med start date	Known	Not TEAE
	Partial	Not TEAE
	Missing	Not TEAE
Partial, could be on or after study med start date	Known	If stop date < study med start date, then not TEAE If stop date >= study med start date, then TEAE
	Partial	Impute stop date as latest possible date (i.e. last day of month if day unknown or 31st December if day and month are unknown), then: If stop date < study med start date, then not TEAE If stop date >= study med start date, then TEAE
	Missing	Assumed TEAE
Missing	Known	If stop date < study med start date, then not TEAE If stop date >= study med start date, then TEAE

START DATE	STOP DATE	ACTION
	Partial	Impute stop date as latest possible date (i.e. last day of month if day unknown or 31st December if day and month are unknown), then: If stop date < study med start date, then not TEAE If stop date $\geq$ study med start date, then TEAE
	Missing	Assumed TEAE

## Algorithm for TEAEs by Study Phase for Onset

TEAE START DATE	ACTION
Known	If start date < week 8 visit date, then TEAE in treatment phase If week 16 visit date $\geq$ start date $\geq$ week 8 visit date, then TEAE in extension phase If start date $>$ week 16 visit date, then TEAE in follow up phase
Partial, but known components can determine the phase	If start date < week 8 visit date, then TEAE in treatment phase If week 16 visit date $\geq$ start date $\geq$ week 8 visit date, then TEAE in extension phase If start date $>$ week 16 visit date, then TEAE in follow up phase
Partial and known components can not determine the phase	Missing day - Impute the 1st of the month unless month is same as month of first dose of study drug then impute first dose date Missing day and month – impute 1st January unless year is the same as first dose date then impute first dose date  If the imputed start date < week 8 visit date, then TEAE in treatment phase If week 16 visit date $\geq$ imputed start date $\geq$ week 8 visit date, then TEAE in extension phase If imputed start date $>$ week 16 visit date, then TEAE in follow up phase
Other missing status	impute first dose date and treat the onset of TEAE as in treatment phase

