1.3 Study Design

This is an 8+8 weeks, randomized, double-blind, multi-center, placebo controlled, parallel group study to include adult patients with moderate to severe active Ulcerative Colitis. The study consists of an 8-week blinded treatment phase, followed by 8-week of blinded active arms extension phase. The primary endpoint is assessed at the end of treatment phase at week 8.

Eligible subjects will be randomized to either one of the 3 doses of active drugs or placebo in 1:1:1:1 ratio for 4mg QD, 4mg BD, 8mg QD and placebo group respectively for treatment phase. The total number of subjects to be randomized is 152. There will be a total of 9 outpatient clinic visits. Subjects randomized into placebo in treatment phase will also have a pre-assigned randomized treatment sequence for extension phase, which are 3 active groups (placebo -> 4mg QD, placebo -> 4mg BD, and placebo -> 8mg QD) in a 1:1:1 ratio. Subjects randomized to the active arms for treatment phase will remain in the same dose group in the extension phase.

At Visit 1 (screening), subject will be screened and if the subject meets the inclusion/exclusion criteria, the subject can be consented and enrolled into the study with a subject identifier number.

At Visit 2 (Day 0), subject will be randomized into the study if there is no further change to subject's criteria.

After randomization, the subject will be followed-up at week 1, week 4, and week 8, corresponding to Visit 3, Visit 4, and Visit 5 at treatment phase respectively. At Visit 5 (week 8) the primary endpoint assessment will be conducted. Following this treatment phase, subjects have the option to enroll into a further 8 weeks of active arms extension phase.

All subjects that have completed the initial 8 weeks (non-responders or responders) have the option to enter a blinded active arm 8-week extension phase according to the group they were randomized to for extension phase. All subjects have the option not enrolling into the extension phase after first 8 weeks of treatment. All subjects in the extension phase are followed-up for further 2 weeks until week 18 (last visit). Subjects who have completed the first 8-week of treatment phase, but decided not entering into extension phase are required to attend the 2-week follow-up visit. Early withdrawn subjects during the first treatment phase cannot enter the extension phase.

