5.8 Early Withdrawal

The definition of an early subject withdrawal from the study will be any subject who is randomized to double-blind medication and, for any reason, is withdrawn prior to completion of the Visit 5 procedures.

A subject may voluntarily discontinue participation in the study at any time. The investigator may also, at his/her discretion; discontinue the subject from participating in the study at any time. In addition, the investigator must make every effort to have the subject return to the clinic as soon as possible after discontinuation of study drug for an Early Withdrawal Visit. An Early Withdrawal Visit may occur at a regular scheduled clinic visit or between clinic visits. The following evaluations and procedures should be completed and recorded in the eCRF.

- Concomitant medication assessment
- AE/SAE assessment

- Physical examination (recorded in source documents only)
- Vital signs
- Collect and review electronic diary
- Collect used study medication (blinded study medication)
- Assess compliance with investigational drug
- 12-Lead ECG
- Laboratory assessments (including chemistry, haematology, and pregnancy test for females of childbearing potential and routine urinalysis)
- Call IVRS to report subject's early withdrawal from the study
- Endoscopy, Mayo score, 9-point modified Mayo score, and partial Mayo score, if feasible.

A subject that is withdrawn from the study after being randomised to treatment cannot be re-screened and subjects who are withdrawn from the study will not be replaced. If the subject withdraws from the study, and also withdraws consent for disclosure of future information, no further evaluations should be performed, and no additional data should be collected. The sponsor may retain and continue to use any data collected before.

Thyroid specific criteria:

Subjects with deranged TSH level (outside of normal range) only, but normal free T4 or free T3. Investigator can follow-up the subject with thyroid function test and assess clinically in 4 weeks.

Deranged TSH level, with associated deranged free T4 and/or free T3(outside of normal range), the investigator should assess subject's clinical condition and decide if the subject should be withdrawn.

Subject with signs and/or symptoms suggestive of hypothyroidism or hyperthyroidism should have laboratory thyroid function performed. If any of the thyroid parameters (TSH, free T4, or free T3) were outside of normal range, the subject is to be withdrawn.

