Reference: CS\_WI\_BS005

phase after first 8 weeks of treatment. All patients in the extension phase are followed-up for further 2 weeks until week 18. Patients who have completed the first 8-week of treatment phase, but decided not entering into extension phase are required to attend the 2-week follow-up visit. Early withdrawn patients during the first 8-week treatment phase cannot enter the extension phase. Early withdrawal visit should be done within 2 weeks after last dose/decision of withdrawal. The total duration of the study participation, including extension and follow-up, will be approximately 18 weeks.

At the baseline visit, patients with moderate-to-severe active ulcerative colitis, with a modified 9-point Mayo score of 5 to 9 points and endoscopic subscore of 2 to 3, and fulfilling all the inclusion/exclusion criteria will be randomized into one of the four treatment arms for the treatment phase: 4mg QD, 8mg QD, 4mg BD of SHR0302 or placebo. All the patients will be stratified according to whether they have previously exposed to anti-TNF $\alpha$ /biological treatment. Patients randomized into placebo in treatment phase will also have a pre-assigned randomized treatment sequence for extension phase, which are 3 active groups (placebo -> 4mg QD, placebo -> 4mg BD, and placebo -> 8mg QD) in a 1:1:1 ratio. Patients randomized to the active arms for treatment phase will remain in the same dose group in the extension phase.

Primary endpoint assessment will be conducted at week 8. 9-point modified Mayo score is the Mayo score excluding physician global assessment (PGA) subscore. 9-point modified Mayo score will be collected as the primary endpoint. This has been advised by the US FDA according to FDA guidance on ulcerative colitis trial. At the completion of the first 8-week treatment period, all patients, responders or non-responders, have the option to enter a blinded active arms 8-week extension phase according to the group they were randomized to for the extension phase. The end-of-study is defined as the date of the last patient's last visit or the actual date of follow-up visit/contact, whichever is later. The study design diagram is provided in below figure (Figure 1).

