## 6.5 WINDOWING CONVENTIONS

No visit windowing will be performed in the statistics for this study.

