### **16.1.1 All TEAEs**

An overall summary of TEAEs in treatment phase will be provided. The number and percentage of patients experiencing AEs and the number of TEAEs will be tabulated.

Incidence of TEAEs will be presented by System Organ Class (SOC) and Preferred Term (PT) and summarized in treatment phase for each SHR0302 dose level , placebo and overall.

All TEAEs during the whole study period will also be summarized for the following groups similarly.

- 8 mg QD total: 8mg QD during the whole study period+ Placebo->8mg QD group after treatment phase
- 4 mg BD total: 4 mg BD during the whole study period + Placebo->4mg BD group after treatment phase
- 4 mg QD total: 4 mg QD during the whole study period + Placebo->4mg QD group after treatment phase
- Placebo only: Placebo group during treatment phase

Incidence of TEAEs will also be broken down further as shown in the following sections.

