### Presentation of Treatment Groups

For outputs, treatment groups will be represented as follows and in that order:

Treatment Group	For Tables, Listings and Graphs
SHR0302 8mg QD during the whole study period	8mg QD
SHR0302 4mg BD during the whole study period	4mg BD
SHR0302 4mg QD during the whole study period	4mg QD
Initially randomized to Placebo	Placebo
Placebo during the treatment phase and SHR0302 8mg QD after treatment phase	Placebo->8mg QD
Placebo during the treatment phase and SHR0302 4mg BD after treatment phase	Placebo->4mg BD
Placebo during the treatment phase and SHR0302 4mg QD after treatment phase	Placebo->4mg QD
Screen failure	Screen failure

For some tables related to TEAE and ECG markedly abnormal criteria, treatment group will be presented as follows.

Treatment Group	For TEAE and ECG Markedly Abnormal Criteria Tables
SHR0302 8mg QD during the whole study period+ Placebo->8mg QD group after treatment phase	8mg QD total
SHR0302 4mg BD during the whole study period + Placebo->4mg BD group after treatment phase	4mg BD total
SHR0302 4mg QD during the whole study period + Placebo->4mg BD group after treatment phase	4mg QD total

Treatment Group	For Tables, Listings and Graphs
Placebo group during treatment phase	Placebo only

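### SAP Appendix 1 puts the wrong placebo switchers in the '4mg QD total' safety column, and Appendix 2 gives no valid phase to dated adverse events in patients withdrawn without a Week 8 visit

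*SAP*

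**What the plan says.** **Column definition.** SAP 16.1.1 sets up pooled columns for the whole-study TEAE tables. For the low dose it reads "4 mg QD total: 4 mg QD during the whole study period + Placebo->4mg QD group after treatment phase". The table under Presentation of Treatment Groups in SAP Appendix 1 defines the same label as "SHR0302 4mg QD during the whole study period + Placebo->4mg BD group after treatment phase". The '4mg BD total' row of that table also takes the Placebo->4mg BD switchers. The comparator column in 16.1.1 is "Placebo only: Placebo group during treatment phase". These labels recur in the tables for relationship, severity, serious infection, discontinuation, serious events, fatal events and deaths (SAP 16.1.1.1 to 16.2). They recur in the QTcF tables of SAP 16.4.1, which use them without defining them.

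**Phase rule.** SAP Appendix 2 sorts TEAEs into phases by comparing onset with visit dates. The treatment phase is given by "If start date < week 8 visit date, then TEAE in treatment phase"; the extension and follow-up phases are cut at the Week 8 and Week 16 visit dates. Partial onsets, after imputation where needed, go through the same comparison. The last row sends an onset that is missing altogether to the treatment phase. No row covers a visit that did not take place. SAP 6.5 adds "No visit windowing will be performed in the statistics for this study", and SAP 7.2 imputes nothing unless told to. Protocol 5.8 foresees the patients concerned: an early withdrawal is a randomized subject who "is withdrawn prior to completion of the Visit 5 procedures".

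**The concern.** The two definitions of '4mg QD total' cannot both be programmed. Appendix 1 is the output convention for the TEAE and ECG tables, so a programmer may reasonably follow it. The low-dose column would then carry events from patients taking a different regimen, and patients who did switch to 4mg QD would appear in no total.

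The phase rule leaves a choice to the programmer just where events may be informative. A patient who leaves before Week 8 may have left because of an adverse event, and that event belongs in the treatment-phase tables. If it has no phase, or is put in follow-up, it drops out of them; for a placebo patient it also drops out of 'Placebo only'. SAP 3.1 says the study's data, safety included, will support the choice of one or two doses to take forward.

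**Working it through.** **1. Column composition, side by side**

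| Total column | Switchers under SAP 16.1.1 | Switchers under SAP Appendix 1 |
|---|---|---|
| 8mg QD total | Placebo->8mg QD | Placebo->8mg QD |
| 4mg BD total | Placebo->4mg BD | Placebo->4mg BD |
| 4mg QD total | Placebo->4mg QD | Placebo->4mg BD |

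Read literally, Appendix 1 counts the BD switchers twice and the QD switchers nowhere.

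**2. Size of the column error if Appendix 1 is programmed**

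Inputs: 152 randomized, 8% dropout and 140 evaluable (Protocol 5.1 and 9.2.1; SAP 3.1); allocation 1:1:1:1, and placebo sequences 1:1:1 (Protocol 1.3). The planned total reproduces: 140/0.92 = 152.2, or 152. This figure is not in dispute and is used only for sizing.

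Per arm: 152/4 = 38. Placebo patients per sequence: 38/3 = 12.67. Extension uptake *u* is not given, so a range is shown. With no dropout, the misassigned share of the column is 12.67*u* / (38 + 12.67*u*):

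- *u* = 100%: 12.67/50.67 = 25%
- *u* = 75%: 9.5/47.5 = 20%
- *u* = 50%: 6.33/44.33 = 14%

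If 8% of placebo patients drop out before switching, 12.67 becomes 11.65 and the shares are 23%, 19% and 13%.

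Because the sequences are allocated equally, the expected column size is the same under either definition. The denominator alone would not reveal the error.

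**3. Phase rule on test cases**

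Take visits at Day 56 and Day 112. Where both took place, the rule works: onset on Day 30 is treatment, Day 70 extension, Day 115 follow-up.

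Now take a patient withdrawn before Week 8, with onset on Day 10 and neither visit:

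- If a comparison with a missing date is undefined, no condition is met and there is no phase.
- If a missing date counts as the lowest value (an assumption about the coding), Day 10 is not before the Week 8 date, the extension condition fails, and Day 10 is after the Week 16 date. The event goes to follow-up.

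Neither result is treatment phase.

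**4. Number of patients exposed to the phase gap**

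Planned dropouts: 152 - 140 = 12, or 12/4 = 3 per arm (38 x 0.08 = 3.04). This assumes that every planned dropout lacks a Week 8 visit. It counts patients, not misplaced events, and the documents give no event rate from which to estimate those.

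**The case against.** The strongest reply on the column is that it is one wrong word. SAP 16.1.1 and the other two Appendix 1 rows pair like with like, and the double counting should be noticed in programming. The output templates, which are not in the documents, may already be right. That is fair as to likelihood and is why the point is called a probable slip. It does not remove the contradiction from the SAP text.

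On the phase rule, the reply is that the gap is narrow. Some early withdrawals may have attended Week 8, because the Protocol 5.8 definition turns on completing that visit's procedures. SAP 3.3 reports subjects without Week 8 efficacy results, but that is not the same as having no visit. TEAEs leading to discontinuation and all SAEs are listed separately. All of this stands, and it limits the size, but no rule in the SAP supplies the missing boundary.

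A reader might infer more than the documents support:

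- *That an absent Week 16 visit distorts the tables in the same way.* The extension is optional ("All subjects have the option not enrolling into the extension phase after first 8 weeks of treatment"), and those who "decided not entering into extension phase are required to attend the 2-week follow-up visit", so many patients may lack that visit. But the SAP describes no TEAE table that separates extension from follow-up. Treatment-phase assignment turns on the Week 8 date, and switchers' events after the treatment phase cover both later phases.
- *That events in placebo withdrawals would be charged to an active dose.* Early withdrawals cannot enter the extension, and Appendix 1 defines the switch groups by active drug after the treatment phase.
- *That the extension should start at the first extension dose rather than at the Week 8 visit.* SAP 13 names dosing time and tablet count as diary items but no kit identifier, and Protocol 6.1.2 does not say which kit supplies the Week 8 clinic dose. That boundary is not shown to be derivable.
- *That crude whole-study counts are an error because dose totals are observed longer than placebo.* Exposure is summarized by phase and the treatment-phase tables compare like with like. Exposure-adjusted rates would be a preference.

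**Conclusion.** The point holds in two parts of unequal weight. The main one is that the Appendix 1 definition of '4mg QD total' is wrong as written and contradicts SAP 16.1.1. If programmed, it would fill about 14% to 25% of that column with patients from the wrong sequence, for extension uptake of 50% to 100% and no dropout. The secondary one is that Appendix 2 gives no valid phase to a known or partial onset in a patient withdrawn without a Week 8 visit. That concerns about 3 patients per arm if the whole planned 8% dropout lacks the visit; how many events would move is unknown. That such events go to follow-up, rather than getting no phase, depends on how missing dates are coded.

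The consequences are limited. Safety is not formally compared (SAP 16), all adverse events stay in the listings (SAP 16.1), active-arm whole-study totals do not depend on phase, and efficacy is unaffected. Importance is minor to moderate, but both items should be settled in the SAP text and not left to the programmer.

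**What to change.** **Appendix 1.** Change the '4mg QD total' row so that it takes the Placebo->4mg QD switchers, as in SAP 16.1.1, and check the output templates against it.

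**Appendix 2.** Add one sentence: for patients with no Week 8 visit and no extension dose, TEAE onsets up to and including Day 59 are treatment phase and later onsets are follow-up, the same in all arms. Day 59 is the end of the protocol's Week 8 window (56 + 3 days, Protocol 5.12). The SAP counts the first dose as Day 0 (SAP 6.1), so the two day scales agree.

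The cost is one corrected row, one sentence and a small programming change. No new data are needed, and nothing in the conduct of the trial changes.

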5.12 Time and Event Table

See [Table1](#).**Table 1. Time and Event Table**

[figure not shown]
Period	Screening	Baseline	Treatment Phase		End of Treatment Phase	Extension Phase		End of Extension Phase	Follow-up/EW ¹¹
VISIT	1	2	3	4	5	6	7	8	9
Week	-4 to -1	0	1	4	8	9	12	16	18
Day	-28 to -1	0	7± 2 days	28± 3 days	56± 3 days	63± 2 days	84± 3 days	112± 3 days	126± 5 days
Procedures									
Written Informed Consent ¹	x								
Demography/Medical History	x								
Physical Examination	x	x	x	x	x	x	x	x	x
Chest X-ray ²	x								
Inclusion/Exclusion Criteria	x								
Randomisation Criteria		x							
Study medication dispensing		x		x	x		x		
Study medication accountability				x	x		x	x	x ¹²
Register Visit in IVRS ³	x	x		x	x		x	x	x ¹²
Endoscopy (colonoscopy) ⁴		x ⁴			x				x ¹²
Efficacy Assessments									
Patient Diary ⁵	x	x	x	x	x	x	x	x	x
Mayo Score		x			x				x ¹²
9-point Modified Mayo Score		x			x				x ¹²
Partial Mayo Score		x	x	x	x	x	x	x	x
Safety Assessments									
12-lead ECG	x	x		x	x	x		x	x
Vital Signs ⁶	x	x	x	x	x	x	x	x	x
Adverse Event Assessment ⁷		x	x	x	x	x	x	x	x
Laboratory Assessments									

Period	Screening	Baseline	Treatment Phase		End of Treatment Phase	Extension Phase		End of Extension Phase	Follow-up/EW ¹¹
VISIT	1	2	3	4	5	6	7	8	9
Week	-4 to -1	0	1	4	8	9	12	16	18
Day	-28 to -1	0	7± 2 days	28± 3 days	56± 3 days	63± 2 days	84± 3 days	112± 3 days	126± 5 days
Procedures									
Haematology and Chemistry Tests	X	X	X	X	X	X	X	X	X
Urinalysis	X	X	X	X	X	X	X	X	X
Lipid Profile (Fasting)		X		X	X	X		X	X
TSH, fT4, fT3	X	X	X	X	X	X	X	X	X
QuantiFERON /or T-Spot /or PPD test ⁸	X								
Hep B sur Ag, Hep C Ab, HIV test	X								
Stool culture/ microscopy	X								
CRP	X	X	X	X	X	X	X	X	X
Faecal Calprotectin		X		X	X			X	
Urine Pregnancy Test ⁹		X	X	X	X	X	X	X	X
β-HCG (blood) ¹⁰	X								
FSH ¹⁵	X								
Medication									
Concurrent Medication Assessment	X	X	X	X	X	X	X	X	X

1. Written informed consent must be obtained prior to performing any Visit 1 procedures or initiating any alterations in a subject's medications
2. Only to be performed if there is no chest X-ray or CT scan available within 3 months of Visit 1
3. IVRS is a randomisation machine used to record all the patient visit.
4. Colonoscopy is completed by baseline (visit 2 – Day 0). The duration of time between endoscopy and baseline is no more than -10 days.
5. Subject use an electronic diary to record disease related medical problems experienced during the study.

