6.1.2 Study Drug Administration

Study medication will be self-administered by the subject twice daily, one (2 tablets) in the morning, another (2 tablets) in the afternoon. Approximately 8 - 12 hours between the morning and afternoon doses.

However, at baseline (Day 0) the first dose will be taken in the clinic. At Week 4 and at the end of treatment (Week 8) subjects should take their morning oral dose at the clinic. Study medication may be taken with or without food.

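### SAP Appendix 2 keeps adverse events with onset on the Week 8 visit date out of the treatment phase and, in placebo switchers, counts them under active drug

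*SAP*

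**What the plan says.** SAP Appendix 2, in the algorithm for phase of onset, has three lines for a known start date. The first is "If start date < week 8 visit date, then TEAE in treatment phase". The second covers dates from Week 8 to Week 16 with equality allowed at both ends, and closes "week 8 visit date, then TEAE in extension phase". The third sends anything after the Week 16 visit to follow-up. The same cut-offs apply to partial dates that settle the phase and to imputed dates. No line refers to a dose or a time of day.

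SAP 16.1.1 builds two sets of tables on this rule:
- The by-arm tables are "summarized in treatment phase for each SHR0302 dose level" and for placebo.
- The whole-study tables use columns such as "8 mg QD total: 8mg QD during the whole study period+ Placebo->8mg QD group after treatment phase", set beside "Placebo only: Placebo group during treatment phase".

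The protocol places the Week 8 visit inside the treatment phase. The Time and Event Table (5.12) heads that visit "End of Treatment Phase". Section 1.3 states: "The primary endpoint is assessed at the end of treatment phase at week 8". Section 5.8 counts a subject as an early withdrawal until the Visit 5 procedures are finished. Section 6.1 has extension drug handed out at that same visit.

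**The concern.** The Week 8 examination, blood and urine tests, ECG and colonoscopy look back on about eight weeks of treatment-phase product. If an adverse event is given that day as its onset, the rule files it under the extension, whether or not an extension dose had been taken.

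Two sets of tables are at stake. The treatment-phase tables are the only place where adverse events on drug and on placebo are compared over the same period, and they lose onsets on their own last day. In the whole-study tables, an event that began in a placebo subject before any active dose can be reported as an event on active drug. SAP 3.1 says the efficacy and safety data are to support the choice of one or two doses, so the columns should follow exposure.

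**Working it through.** No stated figure is under test; the check is of a date rule. Take the Week 8 visit as Day 56 and the Week 16 visit as Day 112 (Protocol 5.12) and apply the rule literally.

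| Subject | Day 55 | Day 56 | Day 57 | Day 112 | Day 113 |
|---|---|---|---|---|---|
| Enters extension | treatment | extension | extension | extension | follow-up |
| Completes Week 8, declines extension (no Week 16 date) | treatment | none | none | none | none |

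For the decliner, the second and third lines both need a Week 16 date, so no category can be evaluated from Day 56 on. (Early withdrawals have no Week 8 date either; that is a separate gap in the same algorithm.)

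Where a Day 56 onset ends up:

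| Subject | Treatment-phase table | Whole-study table |
|---|---|---|
| Active arm | lost | kept in own dose total |
| Placebo, enters extension | lost | leaves *Placebo only*, enters an active total |
| Placebo, declines extension | lost | leaves *Placebo only*, enters no column |

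The treatment-phase loss applies the same cut-off to all four arms. In the whole-study table, active arms keep their own Day 56 events and gain the switchers' events, while placebo loses its own.

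**Size.** Inputs: 152 randomized 1:1:1:1 (Protocol 1.3), so 152/4 = 38 on placebo; switchers split 1:1:1, so 38/3 = 12.7 per dose; each active total is then 38 + 12.7 = 50.7. These are upper values, since they take all 38 as reaching Week 8 and entering the extension. The documents give no rate of Week 8-day onsets, so the share r is an assumption.

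| r | Placebo subjects affected (38 × r) | Added to each active total (38/3 × r) |
|---|---|---|
| 1% | 0.38 | 0.13 |
| 2% | 0.76 | 0.25 |
| 5% | 1.9 | 0.63 |
| 10% | 3.8 | 1.27 |

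One moved subject is 1/38 = 2.6 percentage points in the placebo column and 1/50.7 = 2.0 points in an active total. These are subjects with an event moved. The any-event row for placebo falls only if the subject has no other treatment-phase event, but the row for the specific term can fall even so.

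**The case against.** The strongest defence is consistency. SAP 6.2 treats adverse events starting on the first-dose date as post-baseline, and the treatment-emergence table in Appendix 2 includes equality with the drug start date. Giving boundary-day events to the newer treatment is a recognised convention. SAP 13.1 also assumes that a newly dispensed supply is taken from the morning of the dispensing visit, which would make Week 8 an extension dosing day. Protocol 6.1.2 says "At Week 4 and at the end of treatment (Week 8) subjects should take their morning oral dose at the clinic" but not from which supply. So it is not established that every Week 8-day event in a placebo subject followed placebo alone, and that part of the defence stands.

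The convention does not rescue the rule. It is tied to a visit date, not a dose. It removes events from the controlled table for active-arm subjects, whose treatment does not change, and for decliners, who never take an extension dose.

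Other points on that side also stand. Week 8 values remain in the by-visit laboratory, ECG and vital-sign summaries (SAP 16.3 to 16.5), and all adverse events are listed (SAP 16.1). SAP 16 plans no statistical comparison of safety data unless otherwise specified. The whole-study tables already set up to 16 weeks on active drug against 8 on placebo, and the shift runs against the drug, so it does not hide harm.

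A reader might infer three stronger things that the documents do not support:
- *That everything found at Week 8 is moved.* The rule uses onset. An event found at that visit but dated earlier stays in the treatment phase, and the documents do not say how laboratory-detected events are dated.
- *That both comparisons are biased.* The treatment-phase loss falls on all arms, and no direction has been shown.
- *That a third of laboratory-detected and half of ECG- or lipid-detected events are lost.* Those fractions only count scheduled visits (Weeks 1, 4, 8 or Weeks 4, 8). They need an even spread of events and dating to the test, both assumed.

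**Conclusion.** The point holds for events whose recorded onset is the Week 8 visit date. They are excluded from the treatment phase even when they began before any extension dose. The consequence is a non-directional loss in the treatment-phase tables, a directional shift from placebo to active in the whole-study tables, and no category at all for decliners.

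The numbers are likely to be small: about 0.4 to 3.8 of 38 placebo subjects and 0.1 to 1.3 added to each active total. That range rests on an assumed 1% to 10% of subjects with such an onset, all 38 reaching Week 8 and all entering the extension. Dropout lowers both counts, and declining the extension lowers the number added to the active totals. The reading of the rule is certain and the size is not. Correction is worthwhile because it is cheap and because one subject moves an incidence by 2 to 3 percentage points.

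**What to change.** Change the boundary in SAP Appendix 2:
- **Subjects who enter the extension:** use the first extension-phase dose, by date and time where recorded. An onset before that dose, or on the Week 8 visit date with no recorded time showing that it followed the dose, is treatment phase. A later onset, up to the Week 16 visit, is extension phase.
- **Subjects who do not enter:** an onset up to and including the Week 8 visit date is treatment phase, and a later one is follow-up.

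Apply the same boundary to the dose totals and *Placebo only* columns in SAP 16.1 and 16.2. Add a sensitivity tabulation with untimed Week 8-day events under the alternative assignment. Protocol 6.1 and 6.1.2 and SAP 13.1 should be reconciled on which supply covers the Week 8 morning dose, since that decides how many events are in doubt.

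The cost is one SAP rule, its program and one extra table. The inputs are already foreseen: SAP 13.1 uses a first dose date by phase, SAP 13 takes dosing times from the diary, and SAP 16.1 allows for onset times. The downside is that some untimed same-day events that truly followed the first extension dose will be counted in the treatment phase; the sensitivity table shows how many could be.
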